### Additional Predictors

The following variables will be examined for their effect on the relationship between intervention and the primary and secondary outcome measures:

Perceived Self-Efficacy To Carry Out Safer Sex – described above;

Condom Use Skill is measured, separately, for male and female condoms. For each, a total count of number of basic skills observed by a rater is obtained.

Negotiation Skill is measured by (4-point Likert scale) assessor ratings of the extent of 4 basic negotiation skills demonstrated in participants' completion of sexual risk vignettes. A total skill score can be obtained by summing these. A count of # of alternative solutions is generated. A count of # of obstacles identified is generated.

The Condom Barriers Scale (St .Lawrence, Chapdelaine, Devieux et al., 1999) is a 29-item scale with demonstrated reliability and validity. A 5-point Likert scale is used to answer each item. A total score is obtained. The Attitude Toward The Female Condom Scale will be used to assess reluctance to use female condoms.

Monogamy status will be dichotomously rated as Yes/No. It is well established that condom use is more problematic in monogamous relationships; therefore, the association between monogamy status and unprotected penetrative sex will be examined in study analyses.

Frequency of drug use will be measured on the Risk Behavior Survey (RBS). Since drug use affects libido, arousal, self-control, judgment, agility, emotional lability and other functions that influence sexual behavior, it is conceptualized as an impediment to safer sex.

Past and current abuse experience will be assessed. This assessment includes physical, sexual and emotional abuse.

## **11.4 Study Population**

The study will be carried out at approximately 6 MMTP and 6 ODF who can each provide an average of 40 women who have had recent unprotected, heterosexual penetrative sex, within a recruitment period of about 6 months.

## **11.5 Analytic Plan**

### **11.5.1 Testing and estimation**

All testing will be two-sided and significance will be judged at level  $\alpha=0.05$ . Effects will be reported with point estimate and 95% confidence intervals in addition to p-values.

### **11.5.2 Preliminary analysis**

Prior to the analysis of the primary hypothesis, we will examine the distributions of the outcome measures and identify possible outliers. Outliers will be thoroughly checked for collection or entry errors and will not be used in the analysis unless confirmed as correct and valid data. The confirmation will be by an independent evaluator, in consultation

with the principal investigators. The data managers will not have the authority to correct such values without instructions from the principal investigators.

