## **5.7 Replacement of Subjects**

Subjects who withdraw from study after notification of randomization will not be replaced and will be included in all statistical analyses according to the intention to treat (ITT) design.

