### **8.3 Baseline and Follow-Up Assessment Battery**

Participants will be paid in cash or vouchers for completion of the baseline and follow-up assessments. Reasonable and non-coercive reimbursement sums will be determined on a site-by-site basis. All randomized participants will be followed throughout the study in order to maximize follow up rates. If possible, participants should be interviewed in person, including participants who might be incarcerated. The protocol specific assessments (not the Common Assessment Battery or ACASI administered SERBAS) within the Baseline and Follow Up Assessment should be audiotaped. The following instruments will be used at baseline and follow-up:

**8.3.1 Composite International Diagnostic Interview (CIDI):** The substance abuse subsections of the Composite International Diagnostic Interview, Version 2.1 (CIDI-2.1), part of the CTN common assessment battery, will be used to determine whether participants meet DSM-IV criteria for substance abuse or dependence. This is administered at the baseline only.

**8.3.2 Addiction Severity Index-Lite:** The ASI, also included in the CTN common assessment battery, is a standardized, multidimensional, semi-structured, comprehensive clinical interview that provides problem severity profiles and treatment planning information in 6 problem domains commonly affected by substance abuse. These problem domains are: alcohol and substance abuse; medical; psychiatric; legal; family/social; and employment/support. Composite scores for each domain are derived mathematically. A revised version of the 1997 ASI Lite 5th Edition, limited to the items used in the composite scores and some demographic information, will be administered by a research staff member. The full ASI-Lite will be administered at the baseline only.

At the 3-month and 6-month assessment, only the drug and alcohol section will be administered.

**8.3.3 Biologic Measures:** Urine and alcohol screens will be done at the Baseline assessment to substantiate self-report data. The urine drug screen will occur onsite and test for 10 illicit substances. A breathalyzer will be used to screen for blood alcohol concentration (BAC).

**8.3.4 Drug Use and Drug Injection Risk Behavior Assessment:** The RBS drug use and injection practice items will be repeated at the 3 and 6 month follow-up visits.

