#### **8.4 HIV Risk Assessment**

**8.4.1 Sexual and Sexual Risk Behavior Assessment:** The SERBAS (Sexual Experiences and Risk Behavior Assessment Schedule)(Meyer-Bahlburg et al., 1991; Sohler et al., 2000), a psychometrically sound, longstanding, extensively used instrument of the Columbia University HIV Center For Clinical and Behavioral Studies will be the source of our primary outcome measure, number of unprotected (vaginal and anal) penetrative intercourse occasions, as well as other secondary sexual and sexual risk behavior outcomes for the time period of the past 3 months. SERBAS items will include: 1) number of unprotected penetrative intercourse occasions and number of unprotected penetrative intercourse occasions by (main versus casual) partner type; 2) number of partners, gender of partners, HIV serostatus and HIV risk characteristics of partners; and 3) pursuit of HIV testing and counseling. The SADAR (Sex and drug abuse relationship interview) (Calsyn et al., 2000) will be the source of the secondary outcome measure, proportion of drug or alcohol with sex occasions of all sex occasions; and proportion of unprotected occasions of all sex occasions. It should be noted that the use of these items will permit the comparison of results from the women's and men's studies. All items will be administered using the ACASI method. SERBAS items are currently being used in ACASI format in a 1200-person NIMH multi-site intervention study with HIV seropositive IDUs, female sexual partners of IDUs, and men who have sex with men.

We acknowledge the potential for compromised recall posed by our primary outcome assessment of number of unprotected penetrative intercourse occasions during the past 3 months. We acknowledge that this is particularly true if alcohol and drugs are used before sex. However, we maintain that there are compelling precedents for using this outcome and time frame in HIV risk behavior intervention studies with comparable populations. These include: (1) samples of men and women in community-based STD or health clinics in 5 urban areas--including substantial proportions of drug-users (NIMH Multi-site HIV Prevention Trial Group, 1998; Pinkerton et al., 2002); and (2) a sample of

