#### **11.5.6 Intention to Treat Analysis**

The primary analysis will be in the intent-to treat (ITT) sample, consisting of all randomized subjects.

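### Section 11.5.2 excludes outlying counts unless they are confirmed; a true but extreme self-reported count cannot be verified, so valid values may be lost because of their size.

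*Protocol*

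**What the plan says.** Before the primary analysis, section 11.5.2 states that "we will examine the distributions of the outcome measures and identify possible outliers". Such values are to be checked for errors of collection or entry, and they "will not be used in the analysis unless confirmed as correct and valid data". On who decides, it says "The confirmation will be by an independent evaluator, in consultation" with the principal investigators; data managers may not correct such values without the investigators' instructions. The section gives no definition of an outlier, no standard of confirmation, no blinding to arm for this step, and no analysis with the excluded values kept.

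Three other parts of the protocol bear on this rule.

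- **Analysis set.** Section 11.5.6: "The primary analysis will be in the intent-to treat (ITT) sample, consisting of all randomized subjects". Section 5.7 says that even women who withdraw after learning their assignment "will be included in all statistical analyses according to the intention to treat (ITT) design".
- **Source of the outcome.** The primary count comes from the SERBAS. Section 8.4.1: "All items will be administered using the ACASI method". Section 8.3 sets out what is recorded: "The protocol specific assessments (not the Common Assessment Battery or ACASI administered SERBAS) within the Baseline and Follow Up Assessment should be audiotaped". The biologic measures in sections 8.0 and 8.3.3 cover drugs and alcohol only.
- **Missing data.** Section 11.5.7 rests the main models on missingness that does not depend on the unobserved value. It plans multiple imputation in general, and sensitivity analyses for departures from that assumption.

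**The concern.** A rule that discards values unless they are proved right puts the burden of proof on the data. For a laboratory value with a source record this may be workable. For a private recall of sexual occasions over three months, a true but extreme count has no record to be confirmed against. Because counts are bounded at zero and skewed to the right, the values flagged will be mainly the high ones.

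The consequences are these:

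- Observed post-randomization outcomes are removed according to their size, which does not fit an analysis of all randomized subjects.
- The decision may be taken with knowledge of arm. Section 6.3.2 seeks blinding only for the research assistants who conduct assessments.
- An excluded follow-up value becomes missing because of its own magnitude, which is the situation that section 11.5.7 assumes away.
- The baseline count is a covariate in model (1) of section 11.6.1. If it is excluded and not imputed, the woman leaves the primary model.

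**Working it through.** **1. Can a flagged count be confirmed?** The protocol offers these means of checking.

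| Check | Where | What it can show |
|---|---|---|
| Range, consistency and logic checks | 15.1 | Impossible or contradictory entries |
| Total and protected occasions asked separately | 11.3, primary measure | Protected exceeding total |
| Audiotape | 8.3 | Nothing here; the ACASI SERBAS is excepted |
| Urine and breath tests | 8.0, 8.3.3 | Drug and alcohol use only |

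Each relevant check can refute a value. None can establish that a large, internally consistent count is true.

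**2. The protocol's own model.** Section 11.2 takes counts as Poisson. To confirm this reading, I reproduced one cell of its Table 1: 12 sites, 10 groups of 4 per site, ρ1 = 0.40, ρ2 = 0.10, ρ3 = 0.05, means 17 v 16, no over-dispersion. With n = 20 women per arm per site and group size m = 4:

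- Variance factor = [n(1+ρ1)/2 + n(m−1)ρ2 + n(n−m)ρ3]/n² = (14 + 6 + 16)/400 = 0.09.
- Variance of the difference = [0.09×17 + 0.09×16 − 2×0.05×√(17×16)]/12 = 0.110, so SE = 0.332.
- z = 1/0.332 = 3.01, and power = Φ(3.01 − 1.96) = 0.85, as stated.

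**3. Effect of deletion under Poisson.** Take means of 17 (HE) and 15 (SSB), the largest contrast in section 11.2, so RR = 15/17 = 0.882. The pooled mean is 16 and the pooled variance is 16 + 1 = 17. Mean + 3 SD = 16 + 3×4.12 = 28.4. This deletes 0.50% of HE and 0.09% of SSB values, and RR becomes 0.885. The Q3 + 1.5 IQR rule gives the same, and Q3 + 3 IQR changes nothing.

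**4. Is Poisson realistic?** Section 11.2 quotes baseline arm means of 17.4, 13.7 and 20.9 from the trial it draws on. The arm sizes are not given. Assuming 20 to 100 women per arm, the widest gap of 7.2 has a Poisson SE of √((13.7+20.9)/n), which is 1.32 at n = 20 and 0.59 at n = 100. The gap is then about 5 to 12 standard errors between arms compared before intervention. Even as the largest of three gaps, this points to substantial over-dispersion.

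**5. Effect of deletion under over-dispersion.** The assumptions, none from the protocol, are negative binomial counts with variance μ + μ²/k, a proportional effect (15 v 17), one pooled cut-off, and every flagged value deleted. The RR ranges cover the cut-offs mean + 3 SD, Q3 + 1.5 IQR and Q3 + 3 IQR, from 2 million simulated values per arm.

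| k | HE SD, √(17+289/k) | RR after deletion |
|---|---|---|
| 2 | 12.7 | 0.889-0.910 |
| 1 | 17.5 | 0.902-0.927 |
| 0.5 | 24.4 | 0.919-0.946 |
| 0.3 | 31.3 | 0.931-0.964 |

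Across these, 0.4-11.4% of HE and 0.2-9.7% of SSB values are removed. At k = 0.3 the difference of 2.0 falls to 0.3-0.9. In 4,000 simulated trials of 240 per arm (mean + 3 SD), the estimate moved toward or past the null in 71% at k = 1 and 69% at k = 0.5. In the rest it moved away.

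**6. Other effect shapes** (k = 0.5, pooled cut-off, about 0.88 before deletion).

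| Where the effect lies | RR after deletion |
|---|---|
| More abstainers | 0.871-0.878 |
| Lower 80% of women only | 0.789-0.859 |
| Top 10% of women only | 0.972-1.073 |

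With arm-specific cut-offs and a proportional effect, negative binomial RRs stay at 0.866-0.894, about unchanged.

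**The case against.** The strongest defence is that the rule is ordinary data cleaning. It is tied to collection and entry errors, an independent evaluator confirms, and data managers cannot alter values alone. Confirmed as correct and valid could be read as no error found on checking. Some further material exists to check against: screening repeats three Risk Behavior Survey items for the prior 3 and 6 months (section 8.2.1), and women who cannot be interviewed in person may use a paper SERBAS (section 8.0). The cut-off and the blinding of data review are often settled in a statistical analysis plan, which is not at hand.

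Part of this stands. Error checking is legitimate and should stay, and the absence of a cut-off is not in itself the fault. But the protocol fixes the default, and fixes it as exclusion. The lenient reading is possible but is not what the sentence requires.

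Two stronger readings are tempting and should not be drawn.

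- **The highest-risk women are dropped.** The rule excludes values. A woman who loses one follow-up value stays in through the other, because GEE uses all available data. She leaves only if her baseline value or both follow-up values go and are not imputed.
- **The effect shrinks.** Steps 3 and 6 show that it may hardly move, grow or reverse.

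The planned imputation and sensitivity analyses help only in part. Imputation fitted to the retained values learns from a distribution whose upper tail has been cut. The sensitivity analyses probe a possible departure from missing at random, whereas here the plan itself would create one.

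**Conclusion.** The point holds as a defect in the stated rule. Applied as written, section 11.5.2 can exclude genuine high counts because they are high. That conflicts with sections 5.7 and 11.5.6 and breaks the assumption on which section 11.5.7 rests its main models.

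The size is conditional. Under the protocol's Poisson model the bias is negligible (0.882 to at most 0.885). Under assumed over-dispersion, a pooled cut-off, a proportional effect and no flagged value ever confirmed, the rate ratio moves from 0.88 to 0.89-0.96, and single trials shift toward no effect about 70% of the time. Because every flagged value is deleted, this is the rule at its full force; any confirmation would lessen the shift. The figures compare unadjusted arm means, so they indicate the bias in model (1) but do not measure it. Direction depends on the cut-off, the dispersion and where the effect lies, none of which the protocol gives.

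**What to change.** In section 11.5.2, reverse the default: every observed value is kept in the primary analysis unless a collection or entry error is documented. State that the review is done blind to arm and completed before database lock. If the influence of extreme counts is a worry, add a prespecified winsorised or trimmed analysis as a sensitivity analysis only.

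The cost is a few sentences, and legitimate error correction is untouched. The downside is that extreme but valid values remain in the main analysis and may widen the confidence interval.

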### **11.5.3 Demographic and Baseline Characteristics**

The number of participants enrolled into the study will be summarized by CTP site and by intervention group. For participants who are screened but not randomized, a distribution of the reasons for non-randomization will be provided for each site separately and overall. Intervention groups will be described with regard to baseline characteristics, using proportions when the data are categorical, or means and standard deviations when the data are quantitative.

### **11.5.4 Mixed Effects Models**

Mixed Effects Models (MEMs) will be used to analyze continuous outcome measures. The statistical issues arising from clustering of subjects within therapeutic group and within sites requires appropriate statistical methods for analysis of clustered data, namely Mixed Effects Models (MEM). Mixed effects models are sometimes referred to as hierarchical models (Brown & Prescott, 1999; Bryk & Raudenbush, 1992). MEMs are also used to analyze repeated measurements of data over time (Diggle, Liang & Zeger, 1994). In addition, the repeated measurement on an individual over time are usually correlated and thus represent another cluster in addition to the clustering of subjects within a therapeutic group and clustering of therapeutic groups within a site.

The use of MEMs allows us to estimate the random effects corresponding to the participating sites and to explore the relationship between these random effects and site-specific characteristics. In addition, MEMs do not require complete repeated measurements data on all subjects when used to estimate the course of the outcome variable over time. Incomplete or missing data are handled by the model, providing that the missing data are assumed to be “missing at random” [Little and Rubin, 1987].

In all mixed effects models, site (or more explicitly, CTP) will be modeled as a random effect reflecting our desire to make a global inference among all CTPs, as opposed to treating them as fixed effects, which would correspond to local inference related to only the particular CTPs used in the study. The estimated variance of the random effects corresponding to sites and site by intervention interaction will give a measure of the expected variability in the efficacy of the interventions between CTPs. PROC MIXED in SAS® [SAS Institute Inc. Cary, NC] will be used to carry out the MEM analysis.

The design of our study – to conduct each intervention within each CTP site – makes stratification by CTP a significant source of benefit to power. This benefit strongly offsets the detrimental effect of within CTN correlation. We have made adjustments for the fact that within CTP correlation has a detrimental effect on power – by decreasing the effective degrees of freedom associated with an intervention. For example, our design calls for 20 subjects within each CTP to be assigned to each of the two interventions; the within CTP correlation decreases the 40 degrees of freedom to a number that depends on the size of the correlation. (Please note that the group nature of the intervention is another source of decrease in degrees of effective freedom – due to correlation within group). These conditions have been taken into account in the sample size computations. In fact, the larger the within CTP correlation, the better the power is. Stratification by CTP results in a more powerful test – much like the paired t-

test is more powerful than the two-sample t-test when pairs of observations are known to be associated. (The pairs of observations in this study are the means of the outcome for the experimental and control interventions within CTP site). Sample size computations are performed using the exact model that will be used in the analysis. These computations take into account both the (relatively small) detrimental effect of within CTP correlation and its (relatively large) beneficial effect. The interaction between site and intervention effect is treated as random effect with variance  $\sigma^2$ .

The covariance structure for any particular model will be determined by modeling a variety of possible covariance structures. For example, the correlations between repeated measures on an efficacy measure over time will be modeled as auto-regressive correlation of order one or, compound symmetry or, unstructured correlation. Selection of which structure to be used will be based upon review of both Akaike's Information Criteria and Schwarz's Bayesian Criteria. An auto-regressive covariance structure has the property that observations taken close in time are more correlated than observations taken further apart in time. This correlation structure can be combined with either homogeneous or heterogeneous variances of the observations at different times. A compound symmetric covariance structure has the property that all observations are equally correlated, no matter how much time has elapsed between observations. Compound symmetry covariance structure is appropriate for modeling the correlation between subjects within sites and corresponds to a random effect for site. An unstructured covariance has no restrictions on the correlation and the variances of the repeated measurements; however, it does estimate many more parameters than the other two-covariance structures and is often inefficient.

#### **11.5.5 Methods for Categorical and Count Data**

Generalized estimating equations (GEEs) (Diggle, Liang, and Zeger, 1994) will be used to analyze categorical (binary, ordinal, nominal) and count outcome measures. The statistical issues arising from clustering of subjects within a site requires appropriate statistical methods for analysis of clustered binary data just as it is for continuous normal data. The GEE model is appropriate for the Poisson distribution of our primary outcome number of occasions. The GEE methodology allow for the analysis of categorical and count data which may be missing for some subjects either because of a missed week or due to drop-out, thus complete information for all subjects is not needed. The PROC GENMOD in SAS® [SAS Institute Inc. Cary, NC] will be used to carry out these analyses.

#### **11.5.6 Intention to Treat Analysis**

The primary analysis will be in the intent-to treat (ITT) sample, consisting of all randomized subjects.

#### **11.5.7 Missing data and dropout**

We will make any effort to assess all subjects at both follow-up times (3- and 6-months post-intervention). Despite our thorough and proactive approach to taking complete measurements on all randomized study subjects at all time points, we expect that there will be cases when assessments will be incomplete or missing. The analytic strategy in such cases will depend on the nature of the missing pattern and missing data. For example if at a given assessment time a subject has all but a few items of a questionnaire, a prorated score based on the available items will be computed. As another example, when data on a subject are available only at baseline, such subject

cannot be included in the analysis since even the modern statistical methods like Longitudinal Models (described above) require observations on at least two occasions; in such case some imputation is needed for values of the outcome at follow-up. In general, we will use multiple imputation approach based on propensity scores (Lavori et al., 1995). However, for some outcome measures alternative imputation methods might be more appropriate; for example, for the dichotomous secondary outcome measure 'taking condoms from open clinic supplies' it will be more appropriate to impute 'no' for the missing value of subjects who can not be brought to the clinic for assessment.

In the analysis, we plan to use statistical models that do not require complete observations on all subjects (MEM, GEE). However, the validity of the inference based on these models still depends on whether or not the assumptions on which these models are based are satisfied in our data. One important assumption in all these models is that the missing data is missing 'at random', i.e. the missing mechanism does not depend on the value of the unobserved outcome. Unfortunately, this assumption is un-testable in most medical research and in our study as well. One approach to this problem is to assume a model for the missingness mechanism that does depend on the unobserved outcome value and to do the analysis (i.e. estimate the treatment effect) incorporating the assumed model for the missingness. There are parametric and semi-parametric methods for doing so (Diggle et al., 1994; Kenward, 1998; Rotnitzky et al. 1998, Scharfstein et al. 1999; Liu et al. 1999). Comparison of the inferences from assuming various models for the missingness provides a measure of the validity of the efficacy estimate from the model that assumes missing 'at random'. Another approach to sensitivity analysis is based on the computation of a local sensitivity index which measures the change in the estimated intervention effect in a neighborhood of the 'missing at random' model for missingness (Rotnitzky et al. 2001; Ma and Heitjan (in press)). We plan to perform a sensitivity analysis based on these two approaches in order to assess the effect of the assumption of missing 'at random' being violated on the inference regarding the treatment efficacy.

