### **5.6.3 Procedures for Discontinuation**

A subject choosing to withdraw from study, of her own accord, will inform the staff, and be withdrawn, as requested. Such subjects will not be contacted to obtain follow-up assessments.

A subject who is judged, by clinical or research staff, to be placing herself at serious risk for harm by continued study participation will be asked to meet with the CTP Site coordinator and the subject's therapist(s) jointly. The subject, CTP study site coordinator and the subject's therapist(s) will discuss the pros and cons of participation. If the subject chooses to continue, while the coordinator continues to view intervention participation as detrimental, the subject will be withdrawn from intervention but retained in follow-up assessment. As discussed in sections 8.5 and 9.1.3, subjects who are being discontinued will receive crisis intervention from the CTP Site Coordinator and referral for ongoing abuse-protective services, psychiatric treatment and/or other services as needed.

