## 11.6 Analysis of specific hypotheses

### 11.6.1 Primary hypothesis

Hypothesis 1: SSB intervention will significantly outperform the HE condition with respect to decreasing the number of penetrative intercourse occasions that are unprotected.

The following marginal model for outcome of count will be used to test this hypothesis:

$$(1) \quad \log E(Y_{ijkt}) = \beta_0 + \beta_1 X_{ijk} + \beta_2 t + \beta_3 X_{ijk} t + \gamma_1 Z_{1ijk} + \gamma_2 Z_{2ijk}$$

where  $Y_{ijkt}$  is the value of the primary outcome measure at time  $t$ ,  $t=0$  for 3 months post intervention and  $t=1$  for 6 months post-intervention, for the  $i^{th}$  subject in the  $j^{th}$  intervention group (cluster) in the  $k^{th}$  CTP site (strata);  $X_{ijk}$  is intervention indicator ( $X_{ijk}=1$  for the experimental intervention and  $X_{ijk}=0$  for the control intervention);  $Z_{1ijk}$  is the value of the outcome measure prior to intervention;  $Z_{2ijk}$  is the monogamy status prior to intervention. The model parameters will be estimated by GEE (generalized estimating equation) approach that makes use of all available data and takes into account the within site, within treatment group, and within subject correlations in the way insensitive to the specification of correlations.

The regression parameters in this model correspond to intervention effects of interest. For example, statistically significant from 0 parameter  $\beta_3$  indicates that over time the effects of the two study interventions are different;  $\beta_3 < 0$  corresponds to the effect of the experimental intervention increasing over time faster than the effect of the experimental intervention;  $\beta_3 = 0$  corresponds to no difference in the effectiveness of the interventions over time. If  $\beta_3 = 0$ , the parameter  $\beta_2$  estimates the rate of change in the outcome measure from 3 to 6 months post-intervention in the two intervention groups, and the parameter  $\beta_1$  estimates the difference between the experimental and control intervention, which is the same at the two follow-up assessment times.

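### Section 11.5.7 names propensity-score multiple imputation for women with baseline data only; unless it is run separately by arm, which the protocol does not require, it biases the SSB effect in model (1)

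*Protocol*

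**What the plan says.** Section 11.5.7 expects missing data ("we expect that there will be cases when assessments will be incomplete or missing") but gives no rate. It says that a woman with baseline data only cannot enter the longitudinal models, that "in such case some imputation is needed for values of the outcome at follow-up", and then: "In general, we will use multiple imputation approach based on propensity scores". It cites a source and allows other methods for some outcomes. Its one example is a dichotomous secondary outcome; the primary count is not exempted. It does not say what enters the propensity model or whether donors come from the woman's own arm.

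Baseline-only women are likely to arise, and they stay in the analysis:

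- Section 5.6.3, on women who withdraw of their own accord: "Such subjects will not be contacted to obtain follow-up assessments".
- Section 5.7: "Subjects who withdraw from study after notification of randomization will not be replaced and will be included in all statistical analyses".
- Section 11.5.6: "The primary analysis will be in the intent-to treat (ITT) sample, consisting of all randomized subjects".

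Section 11.6.1 describes the primary fit differently: "The model parameters will be estimated by GEE (generalized estimating equation) approach that makes use of all available data". Model (1) has outcomes at 3 and 6 months only, with the baseline count and monogamy status as covariates. Sections 11.5.5 and 11.5.7 also say that GEE and mixed models do not need complete data.

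**The concern.** Propensity-score imputation sorts women by their predicted probability of being missing and fills each gap with an outcome drawn from observed women in the same class. Arm reaches the imputed value only if donors are restricted by arm, or so far as arm happens to separate the classes. When dropout is similar in the two arms, the classes hold both arms alike, even with arm in the propensity model. A missing SSB woman then receives a draw from a mixture of SSB and HE outcomes, and so does a missing HE woman. The imputed part of the data carries no arm effect, and that effect is what model (1) estimates.

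The primary estimate could therefore be biased although the data are missing at random. The sensitivity analyses planned in 11.5.7 would not show this, because they probe departures from missing at random.

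**Working it through.** **Inputs.** From the protocol: 480 women allocated 1:1; 17 versus 15 or 15.5 occasions; two-sided 0.05; Tables 1 and 2 of section 11.2. Assumed: a baseline-only fraction *f* of 10% to 30%, since the protocol gives none.

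**1. Reproduce a stated power.** Take Table 2 (12 sites; three HE and two SSB groups of 8), 17 versus 15.5, over-dispersed, rho1/rho2/rho3 = 0.60/0.15/0.05; stated power 0.85. With *n* women per arm per site and group size *s*, each arm contributes mean × [(1+rho1)/(2n) + (s−1)rho2/n + (n−s)rho3/n].

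- HE (n = 24): 17 × (1.6/48 + 7×0.15/24 + 16×0.05/24) = 1.877
- SSB (n = 16): 15.5 × (1.6/32 + 7×0.15/16 + 8×0.05/16) = 2.180
- Between-arm covariance: 2 × 0.05 × √(17×15.5) = 1.623
- Variance: (1.877 + 2.180 − 1.623)/12/0.80 = 0.2535, so SE = 0.5035
- Power: Φ(1.5/0.5035 − 1.960) = Φ(1.019) = 0.85, as stated.

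**2. Attenuation with pooled donors and equal dropout.** If imputed women in both arms have the same mean *m*, the difference is [(1−f)17 + fm] − [(1−f)15 + fm] = (1−f) × 2. That is 1.8, 1.6 and 1.4 at f = 10%, 20% and 30%.

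**3. Simulation check.** 480 women, 15 versus 17, counts, one follow-up, no clustering, missingness depending on the baseline count, quintile classes, 5 imputations, 600 runs. Share of the true log rate ratio recovered:

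| Missing (HE / SSB) | Pooled, arm not in propensity model | Pooled, arm in propensity model | By arm | Available data |
|---|---|---|---|---|
| 10% / 10% | 0.894 | 0.904 | 1.015 | 1.011 |
| 20% / 20% | 0.773 | 0.796 | 0.996 | 1.001 |
| 30% / 30% | 0.681 | 0.704 | 1.005 | 1.015 |
| 10% / 30% | 0.780 | 0.758 | 1.036 | 1.011 |
| 30% / 10% | 0.746 | 1.111 | 0.965 | 0.999 |

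Equal dropout agrees with 1−f. With unequal dropout and arm in the propensity model, a class pairs women of different baseline counts across the arms, so the error can also exaggerate the effect (1.111).

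**4. What this does to the cell in step 1.** Pooled imputation: shrink the effect and keep the complete-data SE of 0.5035. Available data: keep the effect of 1.5 and multiply *n* and *s* by (1−f).

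| f | Pooled: effect/SE | Power | Available data: SE | 1.5/SE | Power |
|---|---|---|---|---|---|
| 10% | 1.35/0.5035 = 2.681 | 0.76 | 0.516 | 2.908 | 0.83 |
| 20% | 1.20/0.5035 = 2.383 | 0.66 | 0.531 | 2.825 | 0.81 |
| 30% | 1.05/0.5035 = 2.085 | 0.55 | 0.550 | 2.729 | 0.78 |

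The pooled column makes no allowance for imputation noise.

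**5. Cost when run by arm.** In a second simulation (normal-scale outcome, baseline correlation 0.5, 80% power with complete data, 3,000 runs), available-data power was 0.727, 0.695, 0.657 and 0.644 at 15%, 20%, 25% and 30% missing. By-arm propensity imputation gave 0.682, 0.674, 0.618 and 0.581 without bias: a loss of 4.5, 2.1, 3.9 and 6.3 points.

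**The case against.** **The text is silent on arm.** A reader might infer that the protocol draws donors regardless of arm, so that imputed values are generated under no effect. The protocol does not say that. It is silent, the cited source cannot be consulted here, and donor pools and predictors are details commonly left to a statistical analysis plan. This stands. The point is therefore conditional: the named method has this bias unless run by arm. It is still more than a missing detail, because the protocol chose the method, and even the favourable reading costs power for no gain.

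**The method is not rigid.** Section 11.5.7 says that the strategy depends on the pattern of missing data, and the protocol already describes an available-data fit. True, but it does not say which governs the primary result, and the all-randomised statements in 5.7 and 11.5.6 pull toward imputing.

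**Direction.** A reader might infer that the bias always runs toward zero. It does so for similar dropout only. One arm attends five sessions and the other one, so equal dropout cannot be presumed.

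**Baseline relationship.** A reader might infer that the link to the baseline count is destroyed as well. When dropout depends on baseline and is equal in the arms, it barely changes: a slope of 0.47 to 0.49 against a true 0.50.

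**Size.** The second simulation shows losses of 16 to 29 points for pooled donors, but that scenario was set to 80% complete-data power with one follow-up. In this trial a woman seen at either follow-up is not baseline-only, and sections 8.0 and 8.3 describe active efforts to obtain follow-up. For 17 versus 15, the lowest stated power of 0.97 would still be Φ(3.841×0.9 − 1.960) = 0.93 and Φ(3.841×0.8 − 1.960) = 0.87 at 10% and 20%. The 17 versus 15.5 cells are more exposed.

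**Conclusion.** The concern holds in conditional form. The protocol commits to an imputation method that does not model the outcome and does not require it to be run within arm.

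- **Pooled over arms, similar dropout:** about 0.9 to 0.7 of the SSB effect survives at an assumed 10% to 30% baseline-only. In the worked Table 2 cell, power is about 6, 14 and 23 points below the available-data fit.
- **Pooled over arms, unequal dropout:** the bias can go either way (0.76 and 1.11 with arm in the propensity model).
- **Run by arm:** no bias, but about 2 to 6 points of power lost. Baseline-only women contribute no outcome to model (1), so imputing them adds noise and no information.

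These sizes rest on the assumed attrition, missingness driven by the baseline count, and simulations with one follow-up and no clustering. They show the mechanism and its order of magnitude; they do not forecast this trial's result. The wording should be changed, since the change helps on either reading.

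**What to change.** In section 11.5.7, state that the main analysis of models (1) and (2) is the available-data GEE or mixed-model fit already described in 11.5.5, 11.5.7 and 11.6.1. Say how this fits with the all-randomised statements in 5.7 and 11.5.6: every woman with at least one follow-up outcome is analysed as randomised, and baseline-only women are counted and described by arm.

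For any all-randomised imputed analysis, replace propensity-score imputation with outcome-model-based multiple imputation run separately by arm. For counts, use predictive mean matching or an over-dispersed count model. Predictors should be the baseline count, monogamy status, site and the other follow-up count where observed.

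The cost is a change of wording and a different procedure at analysis, with no new data or participants. The small downside is that an explicit imputation model must be specified.
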